2.3 Risk/Benefit Assessment

2.3.1 Known Potential Risks

The major risk associated with use of human tissue, even as a temporary, non-engrafting therapeutic, is the transmission of infectious agents. This risk is minimized through careful donor screening, Good Tissue Practices, and aseptic current Good Manufacturing Practices (cGMP) processing. Decellularization removes any risk of potential graft vs. host reactions. A review of the literature indicates that various cell and tissue based products tested as therapeutics for non-healing wounds show no differences in adverse event profile compared with SC alone. Experience with a 361 HCT/P version of TTAX01 (NEOX CORD) in treating DFU indicated that weekly application to large wounds may have been associated with a slightly higher rate of local tissue infection. This issue was not seen in Phase 2 testing at the lower frequency of every 4 weeks. Phlebotomy is performed twice, at baseline and end of study, which carries a minor risk of discomfort and possible hematoma. There have been no reported cases of infectious agent transmission in more than 53,000 distributed units of

NEOX®/CLARIX® 100 (trade name for amniotic membrane products) or NEOX®/CLARIX® CORD 1K® (trade name for umbilical cord products), nor have any remarkable adverse events or serious adverse events been reported related to these products. The protocol itself carries a small risk of delaying healing by virtue of excluding a range of alternative therapies, however, none of these is of proven benefit in healing the high grade ulcers under study.

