4 STUDY DESIGN

4.1 Overall Design

The hypothesis under study is that one or more applications over 16 weeks of TTAX01, to the wound surface of a well debrided, complex diabetic foot ulcer managed with appropriate antibiotic therapy will result in a higher probability of complete healing than would be expected from management with standard care alone. In this controlled Phase 3 trial, all subjects will receive standard care throughout the entire study, with the option to add one or more additional therapies if healing is inadequate ($\leq 50\%$ reduction in area) after 8 weeks.

Eligible consenting subjects will undergo a baseline aggressive debridement in the operating room to remove infected and devitalized bone and soft tissue. A six week course of systemic antibiotics will be used to resolve baseline infection following recommendations from the Infections Diseases Society of America (IDSA) guidelines. For subjects randomized to the treatment group, TTAX01 will be applied during the surgical procedure to the debrided wound bed at baseline, and if healing is not evident, it will be applied again at intervals no shorter than 4 week or when replacement of dislodged material is necessary. At each visit the wound will be further debrided as necessary for subjects in both groups.

Surgical debridement at the baseline visit will include biopsies of bone for histology and microbiologic testing, at the start and completion of debridement. This debridement may involve resection of necrotic bone and performance of minor amputations. Systemic antibiotics may be given empirically from the first Screening visit, with adjustments made on the basis of culture and sensitivity results. New or recurrent infections will be managed with additional debridement and adjustment or addition of appropriate systemic antibiotics. For subjects randomized to the treatment group, the test article, TTAX01, will be fixed with sutures, staples or both to the debrided wound bed at baseline and again at no less than 4 week intervals over the 16 week treatment period for wounds that do not show evidence of healing. For wounds in this group that do show evidence of healing, additional applications of TTAX01 will be withheld, week by week.

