8.1.4 Treatment Period (Visits 2– 16; 7 ± 2 days)

[Purpose]: To monitor safety and wound healing, adjust antibiotic regimens, and administer treatment. At each visit of Visits 2 through 16, the listed procedures will be performed for the subject based upon status of the wound.

If the subject will discontinue from TTAX01 treatment at any of these visits, the subject should continue with the scheduled visits through the end of the study in order to observe wound status and general safety. If the subject will discontinue from the trial (drop-out), move immediately to the End of Study Visit (Visit 29) and complete all of the procedures listed.

Beginning at Visit 9 (Day 57), if the wound is not \geq 50% reduced in wound area versus the post debridement measurement obtained at the Initial Procedure Visit prior to randomization, the Investigator may begin to utilize adjunctive therapies as explained in Section 6.5.

If at any Treatment Visit the index ulcer is observed to be closed, perform the following procedures:

- Assess adverse events
- Review concomitant medications
- Assess subject compliance regarding off-loading since the last visit
- Obtain photographs of the closed ulcer using the electronic wound imaging and measuring device
- Observe the wound if it is fully epithelialized with no drainage or need for a dressing, record it as closed.

The next visit scheduled will serve as the first consecutive confirmation visit in 14 ± 2 days and will begin the confirmation of closure procedures (refer to Section 8.1.9).

If the wound remains open, conduct the following procedures:

- Assess adverse events
- Review concomitant medications. These will be recorded in the subject's source document, but should only be recorded in the eCRF for the following:
 - All current and past treatments for the index ulcer only
 - Concomitant medications used to treat the index ulcer (e.g., systemic antibiotics for an index ulcer infection) and the peri-ulcer area (such as treatment for erythema, irritation, itching), together with the indication for the medication
 - Concomitant medications used to treat all SAE, and all AE considered "RELATED" to the product will be recorded in the appropriate eCRF.
- Assess subject compliance regarding off-loading since the last visit
- Assess the foot and lower extremity, then assess the index ulcer after removal of the dressing (but do not remove residual TTAX01 in the treatment group).

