 - Determine whether skin and soft tissue infection (SSTI) is present. If not, follow the scheme shown in *Figure 12.1-1* (Appendix)
 - If SSTI is present, without evidence of osteomyelitis, follow the scheme shown in *Figure 12.1-2* (Appendix); withhold TTAX01 application, obtain a deep tissue biopsy for histopathology, culture and sensitivity, and adjust the antibiotic regimen

- (start a 2 week course of antibiotics if none are being taken, or revise antibiotics if still being taken for a previous infection)
- If new, recurrent or persistent osteomyelitis is suspected, follow the scheme shown in *Figure 12.1-3* (Appendix); repeat procedures to diagnose osteomyelitis (PTB plus imaging or scanning). If osteomyelitis is confirmed, follow the procedures for the Initial Procedure Visit, including application of TTAX01 (start a 6 week course of antibiotics if none are being taken, or revise antibiotics if still being taken for a previous osteomyelitis).
- Clean the wound using sterile saline, non-ionic cleanser or a hypochlorous solution.
 Antiseptic agents including hydrogen peroxide, acetic acid, chlorhexidine, povidone/iodine, and cetrimide should not be used.
- The wound should be sharply debrided to remove callus, macerated, necrotic/devitalized/non-viable tissue and purulence observed on the wound edge and wound bed. Debride until the wound edge is clean and sharply defined, with at least punctate bleeding at the edge and wound bed.
- Obtain photograph and measure the area and volume of the wound using the provided electronic wound imaging and measuring device (after debridement, if performed).
- Determine if additional TTAX01 is necessary **only for subjects in the treatment group** who have not achieved closure.
 - Remove any visible sutures or staples from prior treatment.
 - Remnant TTAX01, if present in the ulcer bed following debridement, should be left in place beneath reapplication.
 - TTAX01 may be reapplied following sharp debridement, for the index ulcer displaying the following criteria:
 - When there is no TTAX01 remnant detected one week after each application, suggesting dislodgement.
 - At least four (4) weeks from previous application of TTAX01 under the following conditions:

- o Neither SSTI or osteomyelitis are observed, and
- Wound healing has stalled, defined as no change of the wound surface area compared to the wound surface area at last application, or
- Wound base does not exhibit hyperemic granulation tissue, or

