- o Wound edge is edematous and elevated.
- TTAX01 should be secured in place by sutures or staples.
- TTAX01 must be fenestrated.
- Obtain post-application photograph of TTAX01 using the electronic wound imaging and measuring device
- TTAX01 will be withheld for 3 weeks following each application, and withheld if the wound shows any of the following favorable signs of healing:
 - Presence of TTAX01 tissue remnant
 - Wound base covered by a black or yellow cap/eschar
 - Wound base showing hyperemic granulation tissue
 - Wound showing epithelialization.
- Apply wound dressing including a non-adherent, standard foam pad or alginate dressing
 (e.g., hydrogels, foam dressings, and alginates) that is appropriate for the amount of
 drainage, and a secondary bandage to ensure a moist wound environment, which
 adequately controls exudate and avoids maceration of the surrounding skin.
- Continue with the off-loading device appropriate to the location of the ulcer (preferably with full length boot or total contact cast, unless not appropriate per the physician, in which case a substitute off-loading device can be made with sponsor approval)
- Adjust infection management including antibiotics as needed, as indicated by the results from the microbiology and histopathology bone biopsy.

Schedule the next Treatment Period visit in one week $(7 \pm 2 \text{ days})$ or, if the subject is at Visit 16, schedule the first Weekly Observation Period Visit 17 in one week $(7 \pm 2 \text{ days})$.

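### The re-dosing rules for TTAX01 in Section 8.1.4 contradict themselves and Sections 1.1, 4.1 and 6.1.2 on dislodged material, on remnants and on what counts as stalled healing

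*Protocol*

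**What the plan says.** Section 8.1.4 governs re-dosing at the weekly Visits 2 to 16.

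- **Reapply list, early route.** A new application is allowed "When there is no TTAX01 remnant detected one week after each application, suggesting dislodgement".
- **Reapply list, four-week route.** From four weeks after the last application, re-dosing is allowed when neither soft tissue infection nor osteomyelitis is seen and one of three alternatives holds. The first is "Wound healing has stalled, defined as no change of the wound surface area compared to the wound surface area at last application". The others are a base without hyperemic granulation and an edematous, raised edge.
- **Remnants.** "Remnant TTAX01, if present in the ulcer bed following debridement, should be left in place beneath reapplication".
- **Withhold list.** TTAX01 is to be held back "for 3 weeks following each application, and withheld if the wound shows any of the following favorable signs of healing". The signs are a remnant, a black or yellow cap, hyperemic granulation, and epithelialization.

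Sections 1.1, 4.1 and 6.1.2 set a minimum interval of four weeks and exempt replacement of dislodged material. Section 4.1 also describes re-dosing, this time without repeating that exemption, as "at no less than 4 week intervals over the 16 week treatment period for wounds that do not show evidence of healing". Sections 4.1 and 6.1.2 suspend dosing while healing is evident.

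Section 8.1.4 also points to the decision diagrams in Appendix 12.1, and note e to the Schedule of Activities (1.3) points to a retreatment algorithm in the Appendix and Study Guide. Neither the diagrams nor the Study Guide could be read for this review.

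**The concern.** These rules define what the experimental arm receives. Staff at roughly 23 sites know the allocation and apply the rules week by week. Where one bullet permits an application and another forbids it for the same wound, two sites can act differently and each cite the protocol.

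Two things are at stake. Exposure in the TTAX01 arm may vary by site for reasons unrelated to the wound. And the Per Protocol population in Section 9.3 requires treatment completed as the protocol planned. Where the lists collide, applying and withholding are each compliant under one bullet and deviant under another.

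**Working it through.** **Setting the passages side by side**

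1. *No remnant at one week.* The reapply list permits a new application, and Sections 1.1, 4.1 and 6.1.2 support early replacement of dislodged material. The withhold sentence covers the three weeks after every application and carries no exception. Followed literally, it blocks the replacement that the other text allows.
2. *Remnant present.* Under the withhold list a remnant alone is enough to hold back. The remnant bullet presupposes an application on top of one. If the withhold list governs, routine re-dosing over a remnant never happens and the bullet has no use.
3. *Area larger than at last application.* As an illustration, a wound going from 10 to 14 cm² has changed area, so it fails the literal definition of stalled. It also shows no reduction in area, so the Section 4.1 test points the other way. It may still qualify through the base or edge criterion, but not on area.

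**Two secondary wording points**

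4. *Unchanged area with hyperemic granulation.* The alternatives in the reapply list are joined by *or*, so unchanged area suffices at four weeks if no infection is seen. Granulation alone triggers withholding. One wound meets both lists, and 8.1.4 does not itself say that the withhold list prevails.
5. *Grouping.* The pattern is A and B, or C, or D. It can be read so that the no-infection condition A attaches only to B, the stalled-area route.

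**How many applications each spacing could allow**

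Inputs: initial application at baseline surgery, taken as Visit 1, Day 1; weekly visits; none permitted after Visit 16 (8.1.5).

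- Visit n falls on Day 1 + 7 × (n − 1). Check against the protocol's own anchor: Visit 9 gives 1 + 7 × 8 = Day 57, which agrees with 8.1.4 ("Beginning at Visit 9 (Day 57), if the wound is not"). Visit 16 is 1 + 7 × 15 = Day 106 and Visit 17 is Day 113.
- Minimum 28 days: Days 1, 29, 57 and 85, so **4** at most. The fifth would fall on Day 113, after the last permitted visit.
- Effect of visit windows: three intervals at the upper limit of 9 days total 27 days, short of 28. Four intervals are always needed at scheduled visits, so the ceiling stays at 4.
- Weekly replacement: Visits 1 to 16, so **16** at most. This needs an absent remnant at each of the 15 visits after baseline.

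For scale, subjects who healed in the Phase 2 study averaged 1.5 applications, median 1, range 1 to 3 (Section 2.2).

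**The case against.** The strongest reply is that the text can mostly be read as one rule. Reapplication is something sites *may* do, while withholding is something they *will* do, so the hold wins. That does not rescue the section: the one-week route would then be dead, and so would the remnant bullet in routine re-dosing.

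Other parts of the reply do stand:

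- Three sections exempt dislodged material, so the intent on point 1 can largely be inferred. What remains is that the operative visit section does not carry the exemption.
- Sections 4.1 and 6.1.2 suspend dosing when healing is evident, and 8.1.4 lists granulation as a favorable sign. That largely settles point 4.
- Section 8.1.4 sorts wounds by infection before re-dosing is considered: soft tissue infection without osteomyelitis means withholding, and suspected osteomyelitis has its own pathway. Section 6.1.2 requires debridement and antibiotics before another dose. Point 5 therefore has little practical effect.
- The Appendix 12.1 diagrams and the Study Guide may supply an order of precedence. If so, the text of 8.1.4 still has to agree with them.

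A reader might infer four stronger things that the documents do not support:

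- *That sites will give anywhere from 4 to 16 doses depending on the bullet chosen.* Both are ceilings, and 16 follows from the dislodgement exemption only if the graft is lost every week. The remnant, area and granulation conflicts act at the four-week interval, within 1 to 4 applications.
- *That the protocol reinstates a regimen it calls harmful.* Section 2.3.1 says that "weekly application to large wounds may have been associated with a slightly higher rate of local tissue infection", in hedged terms and about a marketed version of the product. Replacing a lost piece is not a weekly regimen.
- *That the Per Protocol population cannot be formed.* Section 9.3 has the clinical team determine major deviations before database lock.
- *That a wound which shrinks and then plateaus is wrongly classified.* The comparison point, area at last application, is explicit, so this is a design preference rather than a contradiction.

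**Conclusion.** The point holds as an internal contradiction on three matters: the three-week hold against early replacement of dislodged material, a remnant as a bar against a remnant left under a new application, and stalled healing defined so that an enlarging wound fails the area test. The granulation overlap and the and/or grouping are secondary wording points, largely answered elsewhere in the text.

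Its reach is limited. The primary analysis is by intent to treat, so neither the primary test nor the sample size changes. The effect is on consistency of treatment across open-label sites and on having a single standard for treatment completed as planned. It deserves correction because the rules define the experimental arm and the correction is cheap.

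This rests on the written text alone, with the diagrams and Study Guide unseen. The ceilings of 4 and 16 assume applications only at baseline and at scheduled weekly visits. Which rule is clinically right is not judged here.

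**What to change.** Replace the two lists in 8.1.4 with one ordered decision list that states precedence, and bring Sections 1.1, 4.1 and 6.1.2, the Appendix 12.1 diagrams and the Study Guide into line with it. The clinical team needs to decide and state:

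- how the three-week hold and the one-week no-remnant route relate;
- whether a remnant bars reapplication or may lie beneath it;
- how an enlarging wound is classed, so that the area criterion and the Section 4.1 test agree;
- which list prevails when area is unchanged but a favorable sign is present;
- whether the no-infection condition covers every route in the reapply list.

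The cost is a clarification amendment and a site memo, with no new procedures or subjects. Some applications already given may need classifying under the clarified rule, which is best done before the Per Protocol deviations are settled at database lock.

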8.1.5 Weekly Observation Period (Visits 17 - 20; 7 ± 2 days)

[Purpose]: To monitor safety and wound healing and adjust antibiotic regimens

No further applications of TTAX01 are permitted beyond Visit 16. If the wound deteriorates to $\geq 50\%$ compared to the Initial Procedure post debridement wound area measurement, the Investigator may begin to utilize adjunctive therapies as explained in Section 6.5.

If at any Weekly Observation Period Visit the index ulcer is observed to be closed, perform the following procedures:

- Assess adverse events
- Review concomitant medications
- Assess subject compliance regarding off-loading since the last visit
- Obtain photographs of the closed ulcer using the electronic wound imaging and measuring device
- Observe the wound if it is fully epithelialized with no drainage or need for a dressing, record it as closed.

The next visit scheduled will serve as the first consecutive confirmation visit in 14 ± 2 days and will begin the confirmation of closure procedures (refer to Section 8.1.9).

If the wound remains open, conduct the following procedures:

- Assess adverse events
- Review concomitant medications. These will be recorded in the subject's source document, but should only be recorded in the eCRF for the following:
 - All current and past treatments for the index ulcer only
 - Concomitant medications used to treat the index ulcer (e.g., systemic antibiotics for an index ulcer infection) and the peri-ulcer area (such as treatment for erythema, irritation, itching), together with the indication for the medication
 - Concomitant medications used to treat all SAE, and all AE considered "RELATED" to the product will be recorded in the appropriate eCRF.

- Assess subject compliance regarding off-loading since the last visit
- Assess the foot and lower extremity, then assess the index ulcer after removal of the dressing (but do not remove residual TTAX01 in the treatment group).
- Clean the wound using sterile saline, non-ionic cleanser or a hypochlorous solution.
 Antiseptic agents including hydrogen peroxide, acetic acid, chlorhexidine, povidone/iodine, and cetrimide should not be used.
- The wound should be sharply debrided to remove callus, macerated, necrotic/devitalized/non-viable tissue and purulence observed on the wound edge and wound bed. Debride until the wound edge is clean and sharply defined, with at least punctate bleeding at the edge and wound bed. **Leave in place** any TTAX01, regardless of appearance.
- Obtain photograph and measure the area and volume of the wound using the provided electronic wound imaging and measuring device (after debridement, if performed).
- Apply wound dressing including a non-adherent, standard foam pad or alginate dressing
 (e.g., hydrogels, foam dressings, and alginates) that is appropriate for the amount of
 drainage, and a secondary bandage to ensure a moist wound environment, which
 adequately controls exudate and avoids maceration of the surrounding skin.
- Continue with the off-loading device appropriate to the location of the ulcer (preferably with full length boot or total contact cast, unless not appropriate per the physician, in which case a substitute off-loading device can be made with sponsor approval)
- Adjust infection management including antibiotics as needed, as indicated by the results from the microbiology and histopathology bone biopsy.

Schedule the next Treatment Period visit in one week (7 ± 2 days) or, if the subject is at Visit 20, schedule the first Bi-Weekly Observation Period Visit in two weeks (14 ± 2 days).

8.1.6 Bi-Weekly Observation Period (Visits 21 – 23; 14 ± 2 days)

[Purpose]: To monitor safety and wound healing, adjust antibiotic regimens

No further applications of TTAX01 are permitted beyond Visit 16. If the wound deteriorates to $\geq 50\%$ compared to the Initial Procedure post debridement wound area measurement, the Investigator may begin to utilize adjunctive therapies as explained in Section 6.5.

If at any Bi-Weekly Observation Visit the index ulcer is observed to be closed, perform the following procedures:

- Assess adverse events
- Review concomitant medications
- Assess subject compliance regarding off-loading since the last visit
- Obtain photographs of the closed ulcer using the electronic wound imaging and measuring device
- Observe the wound if it is fully epithelialized with no drainage or need for a dressing,
 record it as closed.

The next visit scheduled will serve as the first consecutive confirmation visit in 14 ± 2 days and will begin the confirmation of closure procedures (refer to Section 8.1.9).

If the wound remains open, conduct the following procedures:

- Assess adverse events
- Review concomitant medications.
- Assess subject compliance regarding off-loading since the last visit, if applicable
- Assess the foot and lower extremity, then assess the index ulcer after removal of the dressing (but do not remove residual TTAX01 in the treatment group).
 - Determine whether skin and soft tissue infection (SSTI) is present. If SSTI is present, without evidence of osteomyelitis, obtain a deep tissue biopsy for histopathology, culture and sensitivity, and adjust the antibiotic regimen (start a 2 week course of antibiotics if none are being taken, or revise antibiotics if still being taken for a previous infection)
 - If new, recurrent or persistent osteomyelitis is suspected, determine whether the wound probes to bone, and obtain imaging or scanning. If osteomyelitis is

- confirmed, start a 6 week course of antibiotics if none are being taken, or revise antibiotics if still being taken for a previous osteomyelitis.
- Clean the wound using sterile saline, non-ionic cleanser or a hypochlorous solution.
 Antiseptic agents including hydrogen peroxide, acetic acid, chlorhexidine, povidone/iodine, and cetrimide should not be used.
- The wound should be sharply debrided to remove callus, macerated, necrotic/devitalized/non-viable tissue and purulence observed on the wound edge and wound bed. Debride until the wound edge is clean and sharply defined, with at least punctate bleeding at the edge and wound bed. **Leave in place** any TTAX01 regardless of appearance.
- Obtain photograph and measure the area and volume of the wound using the provided electronic wound imaging and measuring device (after debridement, if performed).
- Apply wound dressing including a non-adherent, standard foam pad or alginate dressing (e.g., hydrogels, foam dressings, and alginates) that is appropriate for the amount of drainage, and a secondary bandage to ensure a moist wound environment, which adequately controls exudate and avoids maceration of the surrounding skin. Alternative therapies are allowed during this period, per Section 6.5.
- Continue with the off-loading device appropriate to the location of the ulcer (preferably with full length boot or total contact cast, unless not appropriate per the physician, in which case a substitute off-loading device can be made with sponsor approval).
- Adjust infection management including antibiotics as needed, as indicated by the results from the microbiology and histopathology bone biopsy.

Schedule the next Observation Period visit for 14 ± 2 days or, if the subject is at Visit 23, schedule the first Long Term Observation period visit in 28 ± 3 days.

